6.20.3. Cytogenetics/FISH

A bone marrow aspirate sample for cytogenetics testing/chromosome analysis/FISH testing for prior positive markers will be obtained to analyze karyotype at screening and whenever a BMA/biopsy is obtained at the completion of the 21-day treatment period of treatment cycles within 6 days **before dosing for each subsequent cycle** (ie, between Day 22 to Day 27 of that cycle), and at the Treatment Discontinuation Visit or at the time of suspected relapse (whichever occurs first).

During the study, a repeat of local testing of bone marrow cytogenetics and FISH for any positive markers is to be completed whenever a BMA/biopsy is obtained. However, if the cytogenetics/FISH results are **'normal'** at screening or at any point during the study, cytogenetic analysis is not required to be repeated except at the Treatment Discontinuation Visit or at the time of bone marrow evaluation for suspected relapse (whichever occurs first).

For the screening assessment, the cytogenetic files **must** be provided to the central reviewers at [REDACTED]. The central review [REDACTED] will provide standardized analysis and reporting for all subjects. Instructions for submission of cytogenetics files to [REDACTED], central reviewer, are provided in Appendix I.

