- ^k All concomitant over-the-counter/prescription medications/procedures, and intravenous medications taken from signing of the informed consent up to 28 days after the last dose of lenalidomide must be recorded on the appropriate CRF.
- ^l Lenalidomide should be dispensed on Day 1 of each cycle. Only enough lenalidomide for 1 cycle of therapy will be dispensed with each cycle of therapy. The first dose of lenalidomide should be taken only after all Day 1 procedures have been completed with the exception of the collection of PK sampling.
- ^m Lenalidomide accountability should be assessed before IP dispensing for each treatment cycle.
- ⁿ A fresh bone marrow aspirate (and/or a fresh bone marrow biopsy paraffin embedded slides) will be collected at screening from all subjects for confirmation of relapsed/refractory disease.
- ^o ***A bone marrow biopsy is required only if a bone marrow aspirate cannot be obtained.***
- ^p A standard cytogenetic metaphase preparation from the fresh BMA must be prepared for the local cytogenetic testing/chromosome analysis including karyotype. The local site will submit the reports of the karyotype, FISH studies, as well as any available data on molecular mutations (FLT3, CEPBA, NPM1, and others including exome sequencing via Foundation Medicine or other sources) if performed to the central reviewer for retrospective review at Screening only. If subjects have a FISH detectable marker, the test should be repeated until CR/CRi and at relapse.

- ^q The screening BMA slide (and/or bone marrow biopsy paraffin embedded slide) and peripheral blood smear slide **must** be provided to the central reviewers at the [REDACTED]. The central review [REDACTED] will provide standardized analysis and reporting for all subjects. The central reviewer's assessment will be used retrospectively to confirm diagnosis. In the case where a study center has an IRB- and Celgene-approved procedural ICF/IAF that allows collection of additional bone marrow samples for potential research purposes, the latest pre-study PB and BM aspirate/biopsy may be used for screening study assessments.

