- ^r BMA/biopsy and peripheral blood smear must be collected at the completion of the 21-day treatment period within 6 days **before dosing for the subsequent cycle** (ie, between Day 22 to Day 27 of that cycle) in Cycles 1, 2, 3 and 4. If morphologic CR/CRi is achieved within the first 2 cycles, the BMA/biopsy and peripheral blood smear will not be required at the end of Cycle 3. These assessments are required for all subjects at the end of Cycle 4, and at the Treatment Discontinuation Visit or at the time of suspected relapse (whichever occurs first). An IWG response assessment will be performed whenever a bone marrow assessment is performed.
- ^s For subjects who are assessed as having partial response, the BMA/biopsy and peripheral blood smear will be repeated at Cycle 8 **unless** the subject goes to allogeneic HSCT, and at the Treatment Discontinuation Visit or at the time of suspected treatment failure (whichever occurs first).
- ^t During the study, repeat of bone marrow local cytogenetic/FISH testing is to be completed whenever a bone marrow aspirate/biopsy is obtained. However, if the cytogenetics/FISH results are 'normal' at screening or at any point during the study, no further cytogenetic/FISH analysis is required, except at the Treatment Discontinuation Visit or at the time of relapse (whichever occurs first).
- ^u Bone marrow aspirate/biopsy, peripheral blood smear, cytogenetic testing, and an IWG response assessment will be measured at the Treatment Discontinuation Visit or at the time of suspected relapse (whichever occurs first). If clinically inappropriate per the treating site, the subject may have bone marrow evaluation omitted if peripheral blast results are collected.
- [REDACTED]
- [REDACTED]
- [REDACTED]
- [REDACTED]
- ^z Blood PK sampling time points are specified in Table 3. [REDACTED]

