10.6.2. Secondary endpoints

Overall Response Rate

Overall response rate defined as the proportion of subjects with CR, CRi or PR among all subjects evaluable for ORR assessment. The ORR rate at the end of Cycles 1, 2, 3, 4, 8 and 12 will be categorized, and the rate will be calculated by dividing the number of subjects completing each given cycle of interest. The corresponding Clopper Pearson 95% confidence interval will be calculated for the response rate at the end of each pre-specified cycle.

Disease Assessment Outcome

Disease assessment outcome at the end of Cycles 1, 2, 3, 4, 8 and 12 of lenalidomide administered shall be categorized according to the Cheson criteria (Cheson, 2003). The response rate for each of the best response criteria will be calculated as the total number of subjects in a given category at each time point over the number of subjects completing each corresponding cycle. The corresponding Clopper Pearson 95% confidence interval will be calculated per response category at the end of each pre-specified cycle.

Durable Response Rate

Durable response rate is defined as the proportion of subjects achieving a bone marrow confirmed CR/CRi lasting at least 3 months or until transplantation if earlier among all subjects evaluable for the durable response rate assessment. The corresponding Clopper Pearson 95% confidence interval will be calculated for the durable response rate.

Duration of Response

Duration of response is defined as the time from date of the first observed response (CR, CRi or PR) until morphologic relapse, molecular/cytogenetic relapse, or death only for subjects achieving a response. Subjects alive and leukemia-free at the time of the statistical analysis will be censored at the time of their last disease assessment. The median DoR time along with the corresponding 95% confidence interval based on Greenwood's standard error will be calculated using Kaplan-Meier methods. The proportion of subjects remaining without a DoR event at 6, 12 and 24 months will also be presented. Should the number of subjects considered for inclusion in DoR analysis fall below a third of the total sample size, the DoR shall be analyzed descriptively due to the low number of subjects available for analysis. Duration of response shall be analyzed both allowing for censoring of subjects at time of HSCT and without censoring of subjects at the time of HSCT.

Transplantation Rate

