Appendix D: Modified International Working Group AML Response Criteria

Hematologic Response According to IWG Criteria for AML	
Category	Definition
Morphologic Complete Remission (CR)	
The following conditions should be met:
 
 • Absolute neutrophil count (ANC) \geq 1000/μL and platelets \geq100,000/μL without transfusions and/or exogenous growth factor support (ie, no transfusion or exogenous growth factor within 7 days of assessment). • Bone marrow with < 5% blasts and evidence of trilineage hematopoiesis. • No evidence of extramedullary disease.
Morphologic Complete Remission With Incomplete Blood Count Recovery (CRi)	
 • ANC < 1000/μL. • Platelets < 100,000/μL or > 100,000/μL without platelet recovery (requiring transfusion within 7 days of assessment). • Bone marrow with < 5% blasts and evidence of trilineage hematopoiesis. • No evidence of extramedullary disease.
Partial Remission (PR)^a	
 • ANC \geq 1000/μL and platelets \geq 100,000/μL without transfusions and/or exogenous growth factor support (ie, no transfusion or exogenous growth factor within 7 days of assessment). • Bone marrow with 5% to 25% blasts and at least a 50% decrease in bone marrow blast percent from baseline. • No evidence of extramedullary disease.

Hematologic Response According to IWG Criteria for AML	
Category	Definition
Treatment Failure	
Resistant Disease: Patient survives ≥ 7 days post-therapy and failed to achieve CR, CRi, or PR with persistent AML in blood or bone marrow.
 
Aplasia: Patient survives ≥ 7 days post-therapy; death while cytopenic, with aplastic bone marrow.
 
Indeterminate cause:
 
 • Patients who die < 7 days post-therapy. • Patients who die > 7 days post-therapy with no peripheral blood blasts, but no bone marrow examination. • Patients who do not complete the first course of therapy. 
Morphologic relapse after CR or CRi:
 
 • the reappearance of $> 5\%$ blasts in the peripheral blood, or • a single finding of $> 15\%$ blasts in the bone marrow. 
All of the above occurrences should be attributed to relapse following CR or CRi and not attributable to another cause (eg, bone marrow regeneration after consolidation therapy).
 
Molecular or cytogenetic relapse: Reappearance of molecular or cytogenetic abnormality.

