10.2.3. Disease Assessment Outcome

Disease assessment outcome (DAO) at the end of Cycles 1, 2, 3, 4, 8 and 12 of lenalidomide administration shall be categorized according to the Cheson criteria (Cheson, 2003, see Section 18.1) into the following categories: CR, CRi, PR, Treatment Failure (Resistant Disease, Aplasia, Indeterminate Cause, Relapse after CR or CRi, Molecular or Cytogenetic relapse), Missing/not done. Responses occurring after a treatment failure will not be considered. The DAO rate for each of the response criteria will be calculated as the total number of subjects in a given response category at each time point over the number of subjects entering each corresponding cycle. The formula will be the following:

DAO category cycle_i = (number of subjects with DAO category from start of Cycle i Day 1 to the end of Cycle i) / (number of subjects entering Cycle i within the ITT population)*100.

Proportions will be presented as percentages with frequency counts together with the Clopper-Pearson 95% CI, per response category at the end of each pre-specified cycle.

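### Once a cytogenetic/FISH result is normal, retesting at scheduled marrows is optional, yet reappearance of the marker alone counts as treatment failure and as a duration-of-response event

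*Protocol*

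**What the plan says.** **Testing rules (Protocol)**

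- Section 6.20.3, default: "a repeat of local testing of bone marrow cytogenetics and FISH for any positive markers is to be completed whenever a BMA/biopsy is obtained".
- Section 6.20.3, waiver after a normal result: "at screening or at any point during the study, cytogenetic analysis is not required to be repeated except at the Treatment Discontinuation Visit". The same sentence names one other exception, a marrow evaluation for suspected relapse.
- Table 2 note t, waiver after a normal result: "no further cytogenetic/FISH analysis is required, except at the Treatment Discontinuation Visit or at the time of relapse". This names FISH as well, and its second exception is relapse rather than suspected relapse.
- Table 2 note p: "If subjects have a FISH detectable marker, the test should be repeated until CR/CRi and at relapse".

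**Event rules**

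- Protocol Appendix D lists molecular or cytogenetic relapse under treatment failure and defines it as "Reappearance of molecular or cytogenetic abnormality". Morphologic relapse is not also needed.
- Protocol Section 10.6.2 measures DoR from the first CR, CRi or PR "until morphologic relapse, molecular/cytogenetic relapse, or death only for subjects achieving a response".
- SAP Section 10.2.3 tabulates outcomes at the end of Cycles 1, 2, 3, 4, 8 and 12. Its treatment-failure subcategories include "Relapse after CR or CRi, Molecular or Cytogenetic relapse".

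**Marrow schedule**

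Protocol Section 6.20.1 requires marrows at the end of Cycles 1 to 4, but not at Cycle 3 if CR/CRi was reached within two cycles. It adds Cycle 8 for partial responders, and discontinuation or suspected relapse. Section 6.22 lets the discontinuation marrow be omitted when the site judges it clinically inappropriate and peripheral blasts are collected.

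**The concern.** A marker can reappear only after it has cleared. The waiver starts at clearance, so it covers the children who are at risk of this event. A child who is normal at screening generally has no marker to reappear, so the gap concerns markers that clear on study.

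Protocol Section 6.20.4 requires an IWG response assessment at every marrow. At Cycles 2 and 4 the site must therefore choose among categories that include cytogenetic relapse, without necessarily having the test that defines it. An unseen reappearance would be recorded as continuing CR/CRi. That makes the per-cycle overall response rate (SAP 10.2.2) and disease assessment outcome look better, and it lengthens DoR. Ascertainment would also vary with when a child stops treatment, which testing rule a site follows and whether the site tests voluntarily.

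**Working it through.** The plan gives no figure for this point, so the check sets the rules against the schedule.

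**1. Scheduled marrows at which the test becomes optional.** Assume the marker clears at the marrow that shows CR/CRi.

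| CR/CRi first seen | Later scheduled marrows | Test optional at |
|---|---|---|
| Cycle 1 | Cycles 2 and 4 (Cycle 3 waived) | 2 |
| Cycle 2 | Cycle 4 (Cycle 3 waived) | 1 |
| Cycle 3 | Cycle 4 | 1 |
| Cycle 4 | none | 0 |

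A partial responder whose marker has cleared could also go untested at Cycle 8.

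**2. Possible delay in dating the event.** Assume 28-day cycles without delays, marrow on Day 22, no suspected relapse, and treatment that ends on Cycle 12 Day 28 with a discontinuation marrow. Day 22 of cycle c is study day (c − 1) × 28 + 22, and Cycle 12 Day 28 is study day 11 × 28 + 28 = 336. Months are days / 30.4375, as in SAP 18.3.1.

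- Reappearance present but untested at Cycle 2: 336 − 50 = 286 days, or 9.4 months.
- At Cycle 4: 336 − 106 = 230 days, or 7.6 months.
- At Cycle 8 (partial responder): 336 − 218 = 118 days, or 3.9 months.

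The first two exceed the 6-month DoR landmark in Protocol 10.6.2. At the 25% target rate, 0.25 × 43 = 10.75, about 11 complete responders. Ignoring partial responders and censoring, one misdated event would move a landmark proportion by about 1/11, or 9 percentage points.

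**3. Which rule applies.** Take a FISH marker that turns normal before CR/CRi. Note p says to keep testing until CR/CRi. Note t says no further test is required. Section 6.20.3 opens by asking for FISH of previously positive markers whenever an end-of-cycle marrow is taken, and its later waiver relieves only cytogenetic analysis. Sites could reasonably do different things.

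**4. Primary endpoint.** Protocol 10.6.1 counts any CR/CRi within four cycles even if it is later lost. A reappearance after CR/CRi therefore cannot change the Stage 1 or final count. The design probability is the sum over x ≥ 3 of P(X₁ = x) × P(X₂ ≥ max(0, 8 − x)), with X₁ ~ Bin(18, p) and X₂ ~ Bin(25, p). It equals 0.048 at p = 0.10 and 0.800 at p = 0.25, and is untouched by this point.

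**The case against.** The strongest reply is that the plan does not forbid the test. A reader might infer that testing ceases and the event is invisible on treatment. The text does not support that: a repeat is merely not required, sites may test, and testing remains required at discontinuation and at a marrow for suspected relapse. This stands, and it limits the point to incomplete ascertainment. It does not remove it, because a purely cytogenetic relapse need not raise suspicion and the discontinuation marrow can be omitted.

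A reader might also attribute all late dating of DoR to the waiver. That is not supported. After Cycle 4, complete responders have no scheduled marrow until discontinuation or suspected relapse, so retesting on existing marrows would recover only part of the gap.

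Third, a reader might multiply the expected responders by an assumed share with abnormal markers and call the result the number affected. The documents give no such share, and the product would only be a ceiling. An affected child must also clear the marker, respond before Cycle 4, reach a later scheduled marrow on drug, and have the marker return without morphologic or suspected relapse.

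Fourth, the analytic reach is modest. The SAP lists no DoR endpoint (4.2.2), and its Section 16 drops the durable-response summary. Protocol 10.6.2 makes DoR descriptive when fewer than a third of the sample enter it (43/3 = 14.3, against about 11 complete responders at the target rate). All of this stands. DoR nevertheless remains a protocol secondary endpoint, and the per-cycle tables remain in the SAP.

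Finally, a contrast between a child tested on stopping for transplant and one who continues untested is weaker than it looks. DoR is analysed with and without censoring at transplant, and the continuing child is due for testing at his or her own discontinuation or suspected relapse.

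**Conclusion.** The testing rules and the event definitions do not match, and the three statements of the testing rule conflict. Following the plan as written, cytogenetic relapse is undercounted or dated late at up to two scheduled marrows per complete responder (2, 1, 1 and 0 for response at Cycles 1, 2, 3 and 4). The direction favours the drug: longer DoR and better per-cycle response and outcome tables. The 286- and 230-day delays are upper figures under the assumptions stated with them; a child who continues into the extension phase could wait longer. How many children this would touch cannot be derived from the documents. The effect is confined to secondary outcomes, and the 3/18 and 8/43 rules are not affected. The lack of scheduled marrows after Cycle 4 is a separate cause of late dating. The plan should be changed, but the point does not threaten the main conclusion.

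**What to change.** Choose one of two options.

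- **Retest.** Reconcile Section 6.20.3 with Table 2 notes p and t into one rule: a marker that was abnormal at screening is retested locally on each marrow already taken after CR/CRi, whatever the intervening results. Use the same exception (relapse or suspected relapse) throughout. The cost is one or two local tests for a complete responder at Cycles 1 to 3, none for a Cycle 4 responder, and no extra marrow. This leaves the partial responder's Cycle 8 marrow and the molecular component open, unless they are added.
- **Redefine.** Make morphologic relapse and death the main DoR events, and report molecular/cytogenetic relapse separately as incompletely ascertained. This also covers the molecular component, which has no scheduled on-study test: under note p, mutation data are submitted only where available, at screening. It adds no testing, but it changes an endpoint definition and so needs a protocol amendment. The three testing rules should still be made to agree.

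Under either option, add a sentence to SAP 10.1. That section disregards responses that follow a treatment failure. It should state that marker reappearance before CR/CRi does not disqualify a later CR/CRi for the primary endpoint. Otherwise extra testing could remove responses from the primary count. Neither option supplies marrows after Cycle 4, and the report should say so.

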6.20.4. Modified IWG Response

Modified International Working Group response (Appendix D) criteria will be used to assess activity at the completion of predefined treatment Cycles 1, 2, 3 and 4 and at the Treatment Discontinuation Visit or at the time of suspected relapse (whichever occurs first). An IWG response assessment will be performed whenever a bone marrow assessment is performed in order to confirm CR or CRi, PR, or treatment failure. For subjects who are assessed as having partial response, the IWG response will be repeated at Cycle 8 unless the subject goes to allogeneic HSCT, and at the Treatment Discontinuation Visit or at the time of suspected treatment failure (whichever occurs first).

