Grade 3 ALT/AST values that return to levels that meet initial eligibility criteria within 7 days of IP interruption do not require a dose reduction. These subjects may resume treatment at the original dose level. If the toxicity recurs, then dose de-escalation is indicated.

Day 1 of Cycle 2 and beyond may be delayed up to 14 days from the end of the prior cycle in order for subjects to recover from toxicity. If a study interruption has lasted for more than 14 days, the Investigator should contact the Medical Monitor to discuss whether the subject should be continued on the study.

Special Instructions for Myelosuppression:

Due to the underlying marrow infiltrating malignancy, myelosuppression is universal and expected in patients with AML. Therefore, myelosuppression (anemia, neutropenia, and thrombocytopenia) will not require dose reduction or interruption *except* in the case of neutropenia or thrombocytopenia due to prolonged bone marrow aplasia at the end of a treatment cycle in subjects who have achieved remission.

- For subjects who have achieved remission:
 - Prolonged bone marrow aplasia is defined as lack of peripheral blood count recovery to $ANC \geq 500/mm^3$ and platelets $\geq 50,000/mL$ without transfusion for 7 days in the absence of leukemia (bone marrow biopsy demonstrate hypocellularity without evidence of leukemia) at Day 43 of a cycle (ie, failure to start the next cycle within 14 days).
 - The lenalidomide dose will be interrupted and the start of the next cycle will be delayed until count recovery.
 - Prolonged delay (ie, failure to start the next cycle within 14 days) for subjects in remission will require dose de-escalation.
 - If the peripheral blood counts recover within 14 days, the subject will proceed to the next cycle without dose reduction.

- If the peripheral blood counts do not recover within 14 days, repeat bone marrow evaluation including bone marrow biopsy every 7-14 days to assess cellularity and to evaluate for relapse/persistent leukemia.
- For subjects who have not achieved remission:
 - In general, subjects who have not achieved remission and have evidence of residual leukemia will proceed to the next cycle as scheduled regardless of count recovery.
- For subjects with residual leukemia:
 - If residual leukemia is demonstrated and the subject previously had achieved CR/CRi, the subject will be discontinued from the study.

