10.1. Analysis of Primary Efficacy Endpoint

The primary endpoint is the morphological complete response rate within a maximum of 4 cycles of treatment. Morphological complete response is defined as CR or CRi as assessed locally and reported in the "Modified IWG Response Assessment" eCRF page. These response criteria will be assessed according to the revised AML IWG Criteria (Cheson, 2003, see Section 18.1).

The morphological complete response rate is defined as the total number of subjects with morphological complete response observed within the first 4 cycles of study therapy (regardless of whether the CR/CRi is observed at the end of Cycle 1, 2, 3 or 4) over the total number of subjects evaluable for this endpoint. The CR/CRi does not need to be present at the end of Cycle 4 if observed before this time for the subject to be considered as having achieved a complete response with regards to the primary endpoint. Responses occurring after a treatment failure assessment outcome will not be considered. The corresponding Clopper Pearson 95% confidence interval will be calculated for the response rate.

The primary analysis of this endpoint will be based upon the ITT population and the RR population.

Data as collected in the "Modified IWG Response Assessment" eCRF page will be listed.

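### A living, never-remitted child with under 5% marrow blasts, no leukemia and no trilineage hematopoiesis meets no response definition; if coded as treatment failure, a later CR/CRi is dropped from the primary endpoint

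*Protocol*

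**What the plan says.** Protocol 6.20.4: "An IWG response assessment will be performed whenever a bone marrow assessment is performed in order to confirm CR or CRi, PR, or treatment failure". The definitions are in protocol Appendix D, and SAP Table 4 (section 18.1) has the same structure. For the marrow they require:

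- CR and CRi: "Bone marrow with < 5% blasts and evidence of trilineage hematopoiesis".
- PR: "Bone marrow with 5% to 25% blasts and at least a 50% decrease in bone marrow blast percent from baseline".
- Treatment failure, resistant disease: the child "failed to achieve CR, CRi, or PR with persistent AML in blood or bone marrow".
- Treatment failure, aplasia: "death while cytopenic, with aplastic bone marrow".
- Treatment failure, other limbs: death in specified circumstances, a first course not completed, morphologic relapse after CR/CRi, or the return of a molecular or cytogenetic abnormality.

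For the outcome at each cycle, SAP 10.2.3 lists the same categories plus one for missing or not done. SAP 10.2.2, on overall response rate, describes less than PR as treatment failure and disregards responses after a treatment failure. SAP 10.1 applies the same exclusion to the primary endpoint: "Responses occurring after a treatment failure assessment outcome will not be considered".

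Protocol 10.6.1 counts a CR/CRi at the end of any of Cycles 1 to 4 and contains no such exclusion. SAP section 16, which lists changes from the protocol's analysis section, does not mention it.

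**The concern.** Marrow is taken on Day 22 to 27, that is 1 to 6 days after the 21-day dosing block. A marrow cleared of leukemia but not yet showing all three lineages is a plausible finding at that time. The site must then pick a label that the marrow does not meet, and the label decides whether a later remission counts.

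Later remissions are also plausible. Protocol section 4.1 asks investigators to aim for at least 4 cycles. The adult monotherapy study in previously untreated elderly AML, cited in protocol 1.4.1, had a median time to CR/CRi of 30 days (range 1 to 72), so some responses came after the first 28-day cycle.

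SAP 10.1 takes the response as assessed locally, and central review is described for screening and confirmation of diagnosis. Nothing in the documents would harmonise different site choices for the same marrow. The decision rules are 3 of 18 and 8 of 43 responders, so one reclassified child can change either decision.

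**Working it through.** **Step 1: the definitions applied to one child.** The child is alive, has completed the first course, has never had CR/CRi, and has under 5% marrow blasts, no evidence of leukemia and no trilineage hematopoiesis.

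| Outcome | Requirement that fails |
|---|---|
| CR, CRi | trilineage hematopoiesis |
| PR | 5% to 25% blasts |
| Resistant disease | persistent AML |
| Aplasia | death |
| Indeterminate cause | death, or first course not completed |
| Relapse limbs | earlier CR/CRi, or reappearance of an abnormality |
| Missing/not done (SAP 10.2.3) | the assessment was done |

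No row fits.

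**Step 2: what follows from each label if the next marrow, within Cycle 4, shows CR/CRi.**

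- Treatment failure: the later CR/CRi is not counted under SAP 10.1 but is counted under protocol 10.6.1.
- CRi: the child is a responder from the first marrow. If no true CR/CRi follows, this is a false response.
- Missing/not done: the later CR/CRi is counted.

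**Step 3: the plan's design reproduced.** Inputs from protocol 10.3: p0 = 0.10, p1 = 0.25, 18 + 25 = 43 evaluable, continue with at least 3 of 18, declare activity with at least 8 of 43.

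P(go | p) = Σ over x = 3 to 18 of C(18, x) p^x (1−p)^(18−x) × P(Bin(25, p) ≥ 8 − x)

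P(go | 0.10) = 0.0480 and P(go | 0.25) = 0.8003, in line with the stated 5% and 80%. The probability of stopping after Stage 1 is P(Bin(18, p) ≤ 2), which is 13.5% at p = 0.25.

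**Step 4: responders lost.** Let f be the share of true responders coded as treatment failure before their first CR/CRi. This is an assumption; the documents give no figure. The observed rate is 0.25 × (1 − f).

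| f | Observed rate | Power | Stop after Stage 1 |
|---|---|---|---|
| 0 | 0.2500 | 80.0% | 13.5% |
| 1% | 0.2475 | 79.1% | 14.1% |
| 5% | 0.2375 | 75.3% | 16.3% |
| 10% | 0.2250 | 69.7% | 19.5% |
| 20% | 0.2000 | 56.5% | 27.1% |

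**Step 5: responders added.** Let h be the share of true non-responders coded as CRi without meeting it, again an assumption. The observed rate at p0 is 0.10 + 0.90 × h.

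| h | Observed rate | Type I error |
|---|---|---|
| 0 | 0.100 | 4.8% |
| 1% | 0.109 | 7.2% |
| 2% | 0.118 | 10.3% |
| 5% | 0.145 | 23.0% |

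Steps 4 and 5 treat each error alone. They act in opposite directions and could partly offset.

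**The case against.** The strongest reply is that the gap is narrow and neither wrong entry is prescribed. Aplasia needs death, so a living child does not meet it. The phrase equating less than PR with treatment failure is a gloss in the section on overall response rate, not a coding instruction for the primary endpoint. Missing/not done is available and would not trigger the exclusion. The options on the response page of the eCRF are not in the documents. All of this stands, and it means that a responder can be lost, not that one must be. It does not close the gap: missing/not done misdescribes a completed assessment, and nothing directs sites to it.

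Three stronger readings are tempting and are not supported.

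- A reader might infer that any hypocellular leukemia-free marrow is unclassifiable. Appendix D has no cellularity criterion. A hypocellular marrow with under 5% blasts, evidence of trilineage hematopoiesis and low counts can be CRi.
- A reader might infer that protocol 8.2.1 contradicts Appendix D by calling such a marrow a remission. The text there, "bone marrow biopsy demonstrate hypocellularity without evidence of leukemia", is part of a dosing definition for children who have already achieved remission. It does not classify the marrow as a response, so no conflict is shown.
- A reader might infer that children who become aplastic after remission lose their response. They do not: protocol 10.6.1 and SAP 10.1 both keep a CR/CRi once observed. The primary endpoint is at risk only when the unclassified marrow comes before the first CR/CRi.

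The frequency objection also stands. If only 1% of responders are affected, power falls by less than one percentage point.

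**Conclusion.** The concern holds in this limited form. The outcome categories have a gap for a living, never-remitted child past the first course with under 5% blasts, no leukemia and no trilineage hematopoiesis. Read together, SAP 10.2.2 and 10.1 allow that gap to remove a true responder whom protocol 10.6.1 would count, and SAP section 16 does not declare the difference. The opposite error, an unsupported CRi, is also possible.

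The size is unknown. Over the assumed range of 1% to 20% of true responders lost, power is 79.1% to 56.5% against 80.0%. Over 1% to 5% of non-responders logged as CRi, type I error is 7.2% to 23.0% against 4.8%. These figures show sensitivity and are not estimates. The point merits correction because a stated rule can give the wrong primary count against small thresholds and the remedy is cheap.

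**What to change.** Add one outcome to protocol Appendix D, SAP Table 4, SAP 10.2.3 and the IWG response page of the eCRF: under 5% blasts without trilineage hematopoiesis, no evidence of leukemia. State that it is neither a response nor a treatment failure, that it does not trigger the exclusions in SAP 10.1 and 10.2.2, and that the next scheduled marrow decides. A child with no later CR/CRi within Cycles 1 to 4 counts as a non-responder in the primary rate. List the SAP 10.1 exclusion in SAP section 16 as a difference from protocol 10.6.1, or remove it.

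The cost is wording in two documents and, as far as can be judged without seeing the eCRF, one added response option. No extra marrow, no change to treatment rules and no change to sample size is needed. Protocol 8.2.1 needs no edit on this account.
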